9.2.1 Safety observations

The 2 vaccines in this study are both licensed for use in the age group of the study population. Reactions will be documented in order to identify potential differences in the rates of local reactions and/or significant health events between groups.

9.2.2 Immune responses

The manufacturer's criteria for positive test result for HAV (≥ 20 mIU/mL) will be applied in the analysis for each formulation. Quantitative titres will be provided for every positive test result.

9.2.3 Study completion timeline

Field work should be completed within ~16 months of commencing vaccinations and analysis should be completed during the following 1 month. Time required to test sera will likely be 1 month, with data assembly and analysis taking a further 1-2 months. Thus the projected timeline from initial vaccination to full report completion is ~ 18 months.

9.3 Sample size

Assuming seroconversion rates of 35% (midway between 2 adult studies) to standard dose hepatitis A vaccine and 85% to double dose (response after 2 standard doses in adults), a minimum sample size of 36 (18 in each group; alpha 0.05, power 0.80) is required. Assuming that 20% of the population may be immune due to immigration (25% of the Calgary population are immigrants) from an endemic country, and a drop-out rate of 20%, a total of 60 patients will be enrolled.

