Hepatitis A vaccine is given as 2 doses; in healthy pediatric hosts, 97-100% will have a protective response a month after the first dose, therefore they are protected for an imminent trip without completing the 2-dose series. Similar results are documented for all inactivated hepatitis A vaccines, which can be used interchangeably. The second dose is given in 6-12 months to ensure lasting protection. In adults with drug-induced immunosuppression, there are recent publications reporting significantly reduced responses to hepatitis A vaccine. An open label study in adults with rheumatoid arthritis on tumor necrosis factor-inhibitors and / or methotrexate, only 10% had an adequate immune response one month after the first dose. This rose to 83% a month after the second dose. This confirms the deleterious impact of immunosuppressive medications on response to this vaccine, most dramatically so in those on increasingly suppressive regimens. The increase in protective rates after the second dose suggests that given sufficient exposure to antigens in the vaccine, these individuals could mount a much better response. However it is unrealistic for most people to plan and prepare for their trips so far in advance, therefore it would be ideal to find a way of protecting immunosuppressed persons more rapidly, in other words after the first dose. An increased dose of vaccine has been shown to be successful in eliciting a protective immune response to hepatitis B in immunocompromised hosts, such as those on dialysis. There has been success with use of double-dose hepatitis A and B vaccines in such populations (personal communication – [name]).

Bringing these various considerations together, a pilot study of vaccine responsiveness of adolescents on immunosuppressive medications for autoimmune diseases to 2 different doses of Hepatitis A vaccine

will confirm the suboptimal response to this important travel vaccine in a pediatric immunocompromised population, and explore one means of improving it.

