6. VACCINES AND ADMINISTRATION

6.1 Hepatitis A study vaccines

The HAV vaccines to be used in this study will be produced by Sanofi Pasteur (Toronto, ON). Supplies will be obtained from single , following strict cold chain procedures. Each 0.5 mL dose of Avaxim Pediatric® contains 80 antigen units, while Avaxim® (adult) contains double this amount (160 antigen units). Both vaccines contain the following: excipients 2-phenoxyethanol, formaldehyde, aluminum hydroxide (expressed as aluminum to which HAV is adsorbed), Medium 199 Hanks, and polysorbate 80. Manufacturing process residuals include neomycin.

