9. STATISTICAL ANALYSIS

9.1 Choice of outcomes

The **serologic endpoints** will be based on evaluating antibody responses to HAV vaccine. Seroconversion is defined as change from a negative baseline result to a positive test (≥ 20 mIU/mL). A quantitative result will be provided for each positive result.

1. Primary Outcomes: Seroconversion after the first dose of vaccine.
2. Secondary Outcomes: After the second dose of vaccine
 - a) Seroconversion rates
 - b) Titre of seroconvertors

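### Section 9.3 powers the first-dose primary endpoint with a response rate taken from adults after two doses, so the stated 80% power has no support for a single injection

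*Combined protocol and SAP*

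**What the plan says.** Section 9.3 sets the control rate with "Assuming seroconversion rates of 35% (midway between 2 adult studies) to standard dose hepatitis A vaccine" and the comparison rate with "85% to double dose (response after 2 standard doses in adults"). It concludes that "a minimum sample size of 36 (18 in each group; alpha 0.05, power 0.80) is required". It then allows for 20% already immune and "a drop-out rate of 20%, a total of 60 patients will be enrolled".

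Section 9.1 fixes the time point: "Primary Outcomes: Seroconversion after the first dose of vaccine". Section 6.1 defines the arms: "Each 0.5 mL dose of Avaxim Pediatric® contains 80 antigen units, while Avaxim® (adult) contains double this amount (160 antigen units"). So the double dose of section 9.3 is one 0.5 mL injection of the adult formulation, and the day 28 sample after it supplies the primary endpoint. Both arms receive their second injection about six months later.

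The Introduction describes one open-label study in adults with rheumatoid arthritis, in which 10% had an adequate response one month after the first dose. Of the same study it says: "This rose to 83% a month after the second dose". It places the second dose of the usual series 6 to 12 months after the first.

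**The concern.** Section 9.3 itself labels the 85% as a response to two doses, yet applies it to an arm that will have had one injection when the endpoint is read. A second injection given months later is a different stimulus from twice the antigen in one injection. The documents contain no response rate for the latter in immunosuppressed patients.

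The power claim depends on that 85%. If one adult-formulation injection gives a useful but smaller gain, the trial is likely to miss it, and a non-significant dose-1 result could then be taken as evidence that the higher dose does not help. Comparing the formulations after the first dose is part of objective 2, so this is a main result of the study.

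**Working it through.** **Inputs.** From section 9.3: p1 = 0.35, p2 = 0.85, alpha 0.05, power 0.80, 18 per arm. Sidedness is not stated; two-sided is assumed. Section 9.2 names the chi-square test or Fisher's exact test.

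**Step 1: reproduce the plan's figure.** With mean rate p = (0.35 + 0.85)/2 = 0.60 and difference d = 0.50, the uncorrected formula is

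n = [1.960 × √(2 × 0.60 × 0.40) + 0.842 × √(0.35 × 0.65 + 0.85 × 0.15)]² / 0.50² = (1.358 + 0.501)² / 0.25 = 13.8, that is 14 per arm.

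The continuity correction gives

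n' = (13.83/4) × [1 + √(1 + 4/(13.83 × 0.50))]² = 17.6, that is 18 per arm, 36 in total.

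This matches section 9.3 exactly.

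**Step 2: set the source of each rate beside its use.**

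| | Source regimen, as the documents describe it | Where it is used |
|---|---|---|
| 35% | Midpoint of two adult studies, standard dose; one dose is inferred from the contrast with two standard doses | One 80-unit injection |
| 85% | Adults after two standard doses | One 160-unit injection |

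The only detailed adult figures (Introduction) are 10% after one dose and 83% after two. The 85% is close to the second of these and far from the first.

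**Step 3: power if one adult-formulation injection gives less than 85%.** The paediatric arm stays at 35%, as in section 9.3. Power is the sum, over all pairs of counts (a, b), of Bin(a; n, 0.35) × Bin(b; n, p2) wherever the test gives two-sided p ≤ 0.05. The last column takes 24 per arm (see step 4).

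| Adult-formulation rate | 18 per arm: Fisher / chi-square | 24 per arm: Fisher / chi-square |
|---|---|---|
| 85% | 0.84 / 0.92 | 0.94 / 0.97 |
| 80% | 0.73 / 0.84 | 0.86 / 0.92 |
| 75% | 0.61 / 0.74 | 0.75 / 0.84 |
| 70% | 0.48 / 0.62 | 0.62 / 0.73 |
| 60% | 0.25 / 0.37 | 0.33 / 0.45 |

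The chi-square is uncorrected. The rates below 85% are illustrations; the documents supply none.

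**Step 4: does enrolling 60 rescue the power?** The 60 equals 36/(1 − 0.20 − 0.20) = 60. Applying the two losses in turn leaves 60 × 0.8 × 0.8 = 38.4 evaluable, about 19 per arm. If all 60 are already known to be non-immune, as the Investigator Summary can be read, 20% drop-out leaves 60 × 0.8 = 48, or 24 per arm. That helps, but power at 70% is still 0.62 / 0.73. Even with 30 per arm and no losses, power at 60% is only 0.40 / 0.51.

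**The case against.** The best defence is that the 85% is a declared proxy. Section 9.3 names its source openly. The Introduction argues that enough antigen exposure could produce a much better response, and points to higher-dose hepatitis B experience and to a personal communication about double-dose hepatitis A and B vaccines. The study calls itself a pilot, and 36 follows from the stated inputs. All of this stands. It shows that the assumption was deliberate and that testing a higher dose is reasonable. It does not supply a rate: the support is qualitative, and a formal claim of 80% power needs a number for the regimen tested.

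A reader might infer more: that section 9.3 is a whole dose level out, with the 35% belonging to the 160-unit arm. That would follow if the adults' standard dose was the adult formulation. The documents do not name the product or its antigen content, and standard can also be read as standard for age. The mismatch is possible but not established, so reassigning the 35% would replace one unsupported mapping with another. Any power computed that way (for example 0.31 / 0.44 for 10% v 35% at 18 per arm) also needs a rate for 80 units that the documents do not give.

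A reader might also conclude that the trial has 80% power only for differences of about 50 points. That is not general. At 18 per arm the chi-square test has power 0.84 for 35% v 80% and 0.85 for 5% v 45%.

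**Conclusion.** The concern holds for the source of the 85%. Section 9.3 bases the power of a one-injection endpoint on a two-dose response, and nothing in the documents gives a rate that would justify the substitution. This needs no assumption beyond the documents' own wording. The 36 is not an arithmetic error.

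The size is conditional. With 35% on the paediatric arm and 18 per arm, each 5-point shortfall from 85% to 70% costs roughly 0.08 to 0.13 of power, depending on the test, and at 60% the trial would more likely than not miss the difference. The true loss cannot be stated, because no one-injection rate for either formulation in this population is available. If the adults' standard dose was the adult formulation, the 35% would also be in doubt for the 80-unit arm; that remains a question for the sponsor.

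**What to change.** In section 9.3:

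- Stop using the two-dose figure as the basis for a single injection.
- State the assumed one-injection rate for each formulation, by antigen units, with its source. Say which product and antigen content the adult studies used. If no source exists for the higher dose, say that the rate is an assumption.
- State the sidedness and the test, and restate power as conditional on a range of rates, for example the 18-per-arm column of the table above.

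In section 9.2, add that the dose-1 difference in seroconversion will be reported with its confidence interval, so that a non-significant result is not read as no benefit.

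The change is wording only, with no change to doses, visits or enrolment. The price is a less favourable statement of power.

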9.4 Data management

A case report form (source document for local use) will be completed by study personnel at the time of enrolment and each subsequent visit or contact, documenting compliance with the protocol. A study identification number (SID) will be assigned to each subject and used to label the case report form and blood samples. Study personnel will transcribe case information as soon as possible into a secure PC-based electronic case report form (eCRF). Data edits will be checked by a data manager before individual subject files are locked for analysis. Back-up copies of the database will be made whenever new data is entered. No personal identifiers will be included in the database, access to which will be limited by pass code. Data will be viewable by authorized study personnel.

10. OTHER

10.1 Protocol amendment procedures

Any modification of this protocol will be filed and approved by with CHREB. Any administrative changes or amendments to this protocol will apply to all subjects.

